7. ASSESSMENTS

Every effort should be made to ensure that the protocol-required tests and procedures are completed as described. However, it is anticipated that from time to time there may be circumstances outside of the control of the investigator that may make it unfeasible to perform the test. In these cases the investigator will take all steps necessary to ensure the safety and well-being of the subject. When a protocol-required test cannot be performed, the investigator will document the reason for this and any corrective and preventive actions that he or she has taken to ensure that normal processes are adhered to as soon as possible. The study team will be informed of these incidents in a timely manner.

For samples being collected and shipped, detailed collection, processing, storage, and shipment instructions and contact information will be provided to the investigator site prior to initiation of the study.

7.1. Safety Assessments

Safety parameters will be assessed as described in the schedule of activities, and below.

A medical history and physical examination including measurement of vital signs will be performed on all subjects at Visit 1. Significant medical history and observations from the physical examination will be documented in the CRF.

The safety parameters include e-diary reports of local reactions at the 13vPnC injection site and systemic events that occur in the 7 days after investigational product administration. These prospectively collected occurrences of local reactions and systemic events are graded as described in Section 7.1.

Acute reactions within the first 30 minutes after investigational product administration will be assessed and documented in the AE CRF.

In addition, AEs and SAEs are collected, recorded, and reported as defined in [Section 8](#).

7.1.1. Electronic Diary

Subject's parent(s)/legal guardian(s)/caregiver(s) will be required to use an e-diary, based on appropriate technology, and will be asked to monitor and record local reactions and systemic events for 7 days following vaccination (Day 1 through Day 7, where Day 1 is the day of vaccination). The e-diary allows recording of these assessments only within a fixed time window, thus providing the accurate representation of the subject's experience at that time. Local reactions and systemic events will be collected in the e-diary in the evening daily during the e-diary reporting period.

Data on local reactions and systemic events reported on the e-diary will be transferred electronically to a third-party vendor, where they will be available for review by investigators and the Pfizer clinicians at all times via an internet-based portal.

At intervals agreed to by the vendor and Pfizer, these data will be transferred electronically into Pfizer's database for analysis and reporting. These data do not need to be reported by the investigator in the CRF as AEs.

Investigators (or appropriately qualified designee) are required to review the e-diary data online at frequent intervals as part of the ongoing safety review. The investigator or designee must contact the subject's parent(s)/legal guardian(s)/caregiver(s) in order to obtain stop dates for any ongoing local reactions or systemic events on the last day that the e-diary was completed. The stop dates should be documented in the source documents and the information entered in the CRF.

7.1.2. Local Reactions

Redness and swelling will be measured and recorded in caliper units (range: 1 to 14) for the first 7 days following vaccination (Days 1 to 7), and then categorized using the scale shown in Table 3. The measurements will then be recorded in the e-diary.

A caliper will be given to the subject's parent(s)/legal guardian(s)/caregiver(s) with instructions for measuring both redness and swelling at the injection site. Each caliper unit is equivalent to 0.5 cm. The parent(s)/legal guardian(s)/caregiver(s) will be asked to measure the largest diameters of the local reaction. Where a caliper measurement is between 2 values, the higher value should be reported. At the time of entry into the e-diary, the parent(s)/legal guardian(s)/caregiver(s) should record the maximum severity of the reaction since the previous entry into the e-diary.

Table 3. Local Reaction Grading Scale

	GRADE 1 mild	GRADE 2 moderate	GRADE 3^a severe
Redness	1 to 4 caliper units (or measuring device units) = 0.5 to 2.0 cm	5 to 14 caliper units (or measuring device units) = 2.5 to 7.0 cm	>14 caliper units (or measuring device units) = >7.0 cm
Swelling	1 to 4 caliper units (or measuring device units) = 0.5 to 2.0 cm	5 to 14 caliper units (or measuring device units) = 2.5 to 7.0 cm	>14 caliper units (or measuring device units) = >7.0 cm
Pain at injection site (tenderness)	Hurts if gently touched (eg, whimpers, winces, protests, or withdraws)	Hurts if gently touched (with crying)	Causes limitation of limb movement

a. Local reactions >14 caliper units (>7.0 cm) should be assessed by the study site.

7.1.3. Systemic Events and Fever

The e-diary will be used to record the presence of systemic events (loss of or decreased appetite, drowsiness, and irritability) daily for 7 days (Day 1 to Day 7) after each vaccination, using the grading scale in Table 4.

A digital thermometer will be given to the subject's parent(s)/legal guardian(s) with instructions on how to measure the child's axillary temperature at home. Axillary temperature will be collected at evening bedtime daily for 7 days (Day 1 to Day 7) after each vaccination, and at any time during the 7 days when fever is suspected. The highest temperature for each day will be recorded in the e-diary.

Fever is defined as a temperature of $\geq 38.0^{\circ}\text{C}$ (100.4°F).

Temperature will be measured and recorded to 1 decimal place and then categorized according to the scale for fever (see Table 4).

Table 4. Grading Scale for Fever and Systemic Events

Fever	38.0°C to 38.4°C 100.4°F to 101.1°F	38.5°C to 38.9°C 101.2°F to 102.0°F	39.0°C to 40.0°C 102.1°F to 104.0°F	>40.0°C >104.0°F
--------------	--	--	--	---------------------

Systemic Events	GRADE 1 Mild	GRADE 2 Moderate	GRADE 3 Severe
Decreased appetite (loss of appetite)	Decreased interest in eating	Decreased oral intake	Refusal to feed
Drowsiness (increased sleep)	Increased or prolonged sleeping bouts	Slightly subdued; interfering with daily activity	Disabling; not interested in usual daily activity
Irritability (fussiness) (synonymous with restless sleep; decreased sleep)	Easily consolable	Requiring increased attention	Inconsolable; crying cannot be comforted

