### 3.5.2.2.2. Fever

The subject's axillary temperature will be recorded in the e-diary for 7 days (Day 1 to Day 7) after each vaccination. The protocol defines fever as a temperature  $\geq 38.0^{\circ}\text{C}$  (or  $\geq 100.4^{\circ}\text{F}$ ). If more than 1 temperature was taken for a subject on the same day, the highest temperature will be recorded in the e-diary.

Fever will be classified for a given day based on the following scale:

- =., if temperature is missing, or otherwise unavailable.
- =0 (absent), if temperature is not missing and  $< 38.0^{\circ}\text{C}$  ( $100.4^{\circ}\text{F}$ ).
- =1, if temperature is  $\geq 38.0^{\circ}\text{C}$  ( $100.4^{\circ}\text{F}$ ) and  $\leq 38.4^{\circ}\text{C}$  ( $101.1^{\circ}\text{F}$ ).
- =2, if temperature is  $\geq 38.5^{\circ}\text{C}$  ( $101.2^{\circ}\text{F}$ ) and  $\leq 38.9^{\circ}\text{C}$  ( $102.0^{\circ}\text{F}$ ).
- =3, if temperature is  $\geq 39.0^{\circ}\text{C}$  ( $102.1^{\circ}\text{F}$ ) and  $\leq 40.0^{\circ}\text{C}$  ( $104.0^{\circ}\text{F}$ ).
- =4, if temperature is  $> 40.0^{\circ}\text{C}$  ( $104.0^{\circ}\text{F}$ ).

Each category of fever will be included as a separate event in summaries of systemic events.

Similar to the derivations specified for local reactions ([Section 3.5.2.1](#)), fever each day and duration of fever will be derived. However, "each day" and "duration" will be limited to temperature  $\geq 38.0^{\circ}\text{C}$  [ $\geq 100.4^{\circ}\text{F}$ ] only.

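### Two fever category limits do not match between °C and °F: 38.5°C and 39.0°C are paired with 101.2°F and 102.1°F, but equal 101.3°F and 102.2°F

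*Protocol*

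**What the plan says.** Protocol 7.1.3, Table 4, sets four fever categories, the first three as paired ranges: "38.0°C to 38.4°C 100.4°F to 101.1°F", "38.5°C to 38.9°C 101.2°F to 102.0°F" and "39.0°C to 40.0°C 102.1°F to 104.0°F". The fourth is above 40.0°C, or above 104.0°F. SAP 3.5.2.2.2 turns the same pairs into codes 1 to 4, with the °F value in brackets after each °C limit, and adds: "Each category of fever will be included as a separate event in summaries of systemic events".

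On measurement, Protocol 7.1.3 says: "A digital thermometer will be given to the subject's parent(s)/legal guardian(s) with instructions on how to measure the child's axillary temperature at home". On precision: "Temperature will be measured and recorded to 1 decimal place and then categorized according to the scale for fever". Neither statement names a unit. The SAP gives the fever threshold as 38.0°C or, alternatively, 100.4°F. Neither document says which unit the e-diary stores, which unit decides the category, or how a value would be converted or rounded.

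**The concern.** The two halves of each pair are presented as equivalent, so a programmer may apply either. They are not equivalent at the lower limits of the second and third categories. A child whose highest reading is 102.1°F is counted at 39.0°C or above by the °F limits, although 102.1°F does not reach 39.0°C.

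This matters more than an ordinary typing slip because these are working cut-offs. Each category is reported as its own event, and systemic events within 7 days of each dose belong to the primary endpoints (SAP 3.1 and 6.1). Two programmers following the text could produce different fever tables from the same °F data.

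**Working it through.** **Inputs.** The °C and °F limits come from Protocol Table 4 and SAP 3.5.2.2.2. Precision of 1 decimal comes from Protocol 7.1.3. The conversions are F = C × 9/5 + 32 and C = (F − 32) × 5/9.

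**Step 1: try to reproduce the printed °F limits from the °C limits.**

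| °C limit | Exact °F | At 1 decimal | Printed °F | Match |
|---|---|---|---|---|
| 38.0 | 100.40 | 100.4 | 100.4 | yes |
| 38.4 | 101.12 | 101.1 | 101.1 | yes |
| 38.5 | 101.30 | 101.3 | 101.2 | **no** |
| 38.9 | 102.02 | 102.0 | 102.0 | yes |
| 39.0 | 102.20 | 102.2 | 102.1 | **no** |
| 40.0 | 104.00 | 104.0 | 104.0 | yes |

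The two failing figures equal the upper limit of the category below plus 0.1°F. That closes the °F scale but departs from the °C cut-offs.

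**Step 2: convert the two failing limits back.** (101.2 − 32) × 5/9 = 38.44°C, which is 38.4 at 1 decimal and so in the first category. (102.1 − 32) × 5/9 = 38.94°C, which is 38.9 at 1 decimal and so in the second.

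**Step 3: find every affected reading.** Each 0.1°F reading from 99.0 to 106.0°F was categorised by the °F limits, and again by the °C limits after conversion and rounding. Only 101.2°F (second category by °F, first by °C) and 102.1°F (third by °F, second by °C) disagree. In the other direction, each 0.1°C reading from 37.0 to 41.5°C, converted to °F and rounded, keeps its category.

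**Step 4: size, under assumptions.** The documents give no temperature distribution. Assume that all readings are in °F and that febrile maxima tail off exponentially from 100.4°F on a 0.1°F grid with mean m. Let r = exp(−0.1/m). With the grid ending at 105.9°F there are 39 points from 102.1°F upward, and the share s of the count at 102.1°F and above that sits exactly at 102.1°F is (1 − r)/(1 − r^39). The increase of the °F-based count over the °C-based count is s/(1 − s).

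| m (°F) | s | s/(1 − s) |
|---|---|---|
| 0.7 | 13.4% | 0.134/0.866 = 15.5% |
| 1.0 | 9.7% | 0.097/0.903 = 10.7% |
| 1.5 | 7.0% | 0.070/0.930 = 7.5% |

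Without an upper end to the grid, the increase is exp(0.1/m) − 1, or 15.4%, 10.5% and 6.9%. The result depends little on where the tail is cut.

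**The case against.** The strongest reply is that nothing goes wrong in practice. °C is written first throughout, neither document mentions °F capture, and °C readings at 1 decimal are categorised correctly. Within each unit the categories are complete at 1 decimal, with no gap or overlap. The study is descriptive, with no hypothesis tests or decision rules (SAP 5.1). All of this stands, and it is why the point is small. It does not make the printed pairs right: the SAP's own wording admits a °F threshold, and no sentence excludes °F entry.

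Three stronger readings are tempting but unsupported:

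- A reader might infer that 101.2°F and 102.1°F receive no category, because 38.44 and 38.94 lie between the °C ranges. That needs an unrounded conversion, which neither document prescribes and which sits badly with the 1-decimal rule.
- A reader might infer that the count of any fever could change. Fever is defined by temperature of at least 38.0°C, not by category code, and 38.0°C and 40.0°C convert exactly. The counts at or above 38.0°C and above 40.0°C are unaffected.
- A reader might infer a bias between the MDV and PFS groups. One rule would be applied to both randomised groups, and the documents give no reason to expect a differential effect.

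**Conclusion.** The point holds as a minor inconsistency in operative cut-offs. Two of the six °F limits that bound the first three categories are 0.1°F below the exact equivalents of their °C partners, in both documents, and no governing unit is stated.

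The effect is zero for °C capture. For °F capture it is confined to readings of exactly 101.2°F and 102.1°F, and it alters only the split between the first and second categories and between the second and third. The figure of about 7.5% to 15.5% for the count at 39.0°C and above rests on assumed °F capture throughout and an assumed exponential tail with mean 0.7 to 1.5°F. It is relative to the °C-based count. The documents give no fever rate, so no number of affected children can be derived from them. No conclusion of the study depends on this, but the tables should follow one rule fixed before programming.

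**What to change.** In SAP 3.5.2.2.2, add one sentence: the °C cut-offs govern fever categorisation, and any reading in °F is converted to °C and rounded to 1 decimal before it is categorised. Correct the °F limits there to 100.4 to 101.2°F, 101.3 to 102.1°F and 102.2 to 104.0°F. With these limits both units give the same category for every reading at 1 decimal.

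The cost is one sentence and four figures in the SAP. No data collection changes, and the fever definition stays as it is. The SAP may refine the protocol's plan (Protocol 9, SAP 2), so this need not wait for the protocol. Align protocol Table 4 at the next amendment; since amendments need ethics committee approval (Protocol 12.1), this point alone does not justify one. Writing the categories as half-open °C intervals is an optional programming style and changes nothing at 1 decimal.

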7.2. Biological Samples

Serum samples will be used only for scientific research. Each sample will be labeled with a code so that the laboratory personnel testing the samples will not know the subject's identity. Samples that remain after performing assays outlined in the protocol may be stored by Pfizer. Unless a time limitation is required by local regulations or ethical requirements, the samples will be stored for up to 15 years after the end of the study and then destroyed. If allowed by the informed consent document, stored samples may be used for additional testing to better understand the immune responses to the vaccine(s) under study in this protocol, to inform the development of other products, and/or for vaccine-related assay work supporting vaccine programs. No testing of the subject's genetic material will be performed.

The subject's parent(s)/legal guardian(s) may request that the child's samples, if still identifiable, be destroyed at any time; however, any data already collected from those samples will still be used for this research. The biological samples may be shared with other researchers as long as confidentiality is maintained and no testing of the subject's genetic material is performed.

7.3. Immunogenicity

Serotype-specific IgG concentrations to the 13 pneumococcal serotypes (1, 3, 4, 5, 6A, 6B, 7F, 9V, 14, 18C, 19A, 19F, and 23F) will be determined in all subjects from the blood sample taken 1 month after the infant series and 1 month after the toddler dose of 13vPnC.

To support the clinical development of Pfizer's pneumococcal conjugate vaccines, a high-throughput, multiplex direct Luminex-based immunoassay (dLIA) platform has been developed to replace the WHO standardized enzyme-linked immunosorbent assay (ELISA) platform. Pfizer's 13-plex dLIA was validated using immunized human serum that contains IgG antibodies against the Prevnar 13 serotypes 1, 3, 4, 5, 6A, 6B, 7F, 9V, 14, 18C, 19A, 19F, and 23F. There are several advantages to using a multiplex assay approach over the WHO reference ELISA for testing clinical samples. While both measure pneumococcal serotype-specific IgG antibodies, the Luminex-based assay is performed in a multiplex format, which generates more results in a shorter period of time, requires less serum, and generates less laboratory waste compared to ELISA. In addition, in part because of its multiplex format, Pfizer's 13-plex pneumococcal dLIA platform accommodates 143 tests on a single assay plate, while the ELISA platform would require 36 assay plates to achieve the same number of tests.

An examination of the percentage of vaccine responders reaching IgG concentrations ≥ 0.35 $\mu\text{g/mL}$ is historically based on the WHO reference ELISA, and the WHO Expert Committee has provided guidance on acceptable bridging strategies for manufacturers that use an alternative assay platform for clinical evaluations. To bridge the validated 13-plex dLIA to the WHO ELISA platform, a comprehensive bridging study was performed using residual serum from pivotal Prevnar 13 studies. On the basis of the bridging data submitted to, and approved by, the US Food and Drug Administration (FDA), an IgG threshold level of 0.35 $\mu\text{g/mL}$ using the 13-plex dLIA platform is appropriate for serotypes 1, 3, 4, 5, 6A, 7F, 9V, 14, 18C, 19F, and 23F, while lower threshold values for the 13-plex dLIA platform are justified for serotypes 5 (0.23 $\mu\text{g/mL}$), 6B (0.10 $\mu\text{g/mL}$), and 19A (0.12 $\mu\text{g/mL}$) in order to maintain the same proportion of vaccine responders reported using the ELISA platform.

Serotype-specific OPA assays for the 13 pneumococcal serotypes will be performed in all subjects from the blood samples taken 1 month after the infant series and 1 month after the toddler dose of 13vPnC, where sufficient sera are available. Results will be reported as antibody titers.

8. ADVERSE EVENT REPORTING

8.1. Requirements

The table below summarizes the requirements for recording safety events on the CRF and for reporting safety events on the Clinical Trial (CT) Serious Adverse Event (SAE) Report Form to Pfizer Safety. These requirements are delineated for 3 types of events: (1) SAEs; (2) nonserious AEs; and (3) exposure to the investigational product under study during pregnancy or breastfeeding, and occupational exposure.

Safety Event	Recorded on the CRF	Reported on the CT SAE Report Form to Pfizer Safety Within 24 Hours of Awareness
SAE	All	All
Nonserious AE	All	None
Exposure to the investigational product under study during pregnancy or breastfeeding, and occupational exposure	All (regardless of whether associated with an AE), except occupational exposure	Exposure during pregnancy, exposure via breastfeeding, occupational exposure (regardless of whether associated with an AE)

All observed or volunteered events regardless of vaccine group or suspected causal relationship to the investigational product(s) will be reported as described in the following paragraphs.

Events listed in the table above that require reporting to Pfizer Safety on the CT SAE Report Form within 24 hours of awareness of the event by the investigator **are to be reported regardless of whether the event is determined by the investigator to be related to an investigational product under study**. In particular, if the SAE is fatal or life-threatening, notification to Pfizer Safety must be made immediately, irrespective of the extent of available event information. This time frame also applies to additional new (follow-up) information on previously forwarded reports. In the rare situation that the investigator does not become immediately aware of the occurrence of an event, the investigator must report the event within 24 hours after learning of it and document the time of his/her first awareness of the event.

For each event, the investigator must pursue and obtain adequate information both to determine the outcome and to assess whether it meets the criteria for classification as an SAE (see the Serious Adverse Events section below). In addition, the investigator may be requested by Pfizer Safety to obtain specific follow-up information in an expedited fashion. This information is more detailed than that recorded on the CRF. In general, this will include a description of the event in sufficient detail to allow for a complete medical assessment of the case and independent determination of possible causality. Any information relevant to the event, such as concomitant medications and illnesses, must be provided. In the case of a subject death, a summary of available autopsy findings must be submitted as soon as possible to Pfizer Safety. Any pertinent additional information must be reported on the CT SAE Report Form; additional source documents (eg, medical records, CRF, laboratory data) are to be sent to Pfizer Safety **ONLY** upon request.

As part of ongoing safety reviews conducted by the sponsor, any nonserious AE that is determined by the sponsor to be serious will be reported by the sponsor as an SAE. To assist in the determination of case seriousness, further information may be requested from the

investigator to provide clarity and understanding of the event in the context of the clinical study.

8.1.1. Additional Details on Recording Adverse Events on the CRF

All events detailed in the table above will be recorded on the AE page(s) of the CRF. It should be noted that the CT SAE Report Form for reporting of SAE information is not the same as the AE page of the CRF. When the same data are collected, the forms must be completed in a consistent manner. AEs should be recorded using concise medical terminology and the same AE term should be used on both the CRF and the CT SAE Report Form for reporting of SAE information.

8.1.2. Eliciting Adverse Event Information

The investigator is to record on the CRF all directly observed AEs and all AEs spontaneously reported by the study subject's parent(s)/legal guardian(s)/caregiver(s). In addition, each study subject's parent(s)/legal guardian(s)/caregiver(s) will be questioned about the occurrence of AEs in a nonleading manner.

8.1.3. Withdrawal From the Study Due to Adverse Events (see also the Subject Withdrawal section)

Withdrawal due to AEs should be distinguished from withdrawal due to other causes, according to the definition of AE noted below, and recorded on the CRF.

When a subject withdraws from the study because of an SAE, the SAE must be recorded on the CRF and reported, as appropriate, on the CT SAE Report Form, in accordance with the Requirements section above.

8.1.4. Time Period for Collecting AE/SAE Information

The time period for actively eliciting and collecting AEs and SAEs ("active collection period") for each subject begins from the time the subject's parent(s)/legal guardian(s)/caregiver(s) provide(s) informed consent, which is obtained before the subject's participation in the study (ie, before undergoing any study-related procedure and/or receiving investigational product), through and including Visit 4 and from Visit 5 to Visit 6.

Between Visit 4 and Visit 5, only newly diagnosed chronic medical conditions and SAEs will be reported. In addition, end dates will be reported for any events ongoing from the previous visit.

